1.6 Study Population

Effectiveness endpoints for this study will be:

- The proportion of subjects with an IOP reduction of 20% or more from baseline at each postoperative visit.
- The proportion of subjects with an IOP reduction of 20% or more from baseline after 6 months while using the same number or fewer medications.

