3.7.5 Follow-up after Adverse Events

Related systemic and all ophthalmic AEs for either eye at any level of potential relatedness (unlikely related, possibly related, probably related, or definitely related) will be followed and documented until complete resolution, resolution with sequelae, until the subject exits from the study for conditions with no possibility of resolution (e.g., iris atrophy, macular degeneration), or for one month after study exit.

Subjects with AEs will continue to be followed according to the protocol, unless continuing to do so would place the subject at undue risk (e.g., if they are hospitalized).

If a subject requires additional glaucoma surgery, the subject will continue to be seen for the duration of the study at required follow-up visits so that safety and effectiveness can continue to be monitored.

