3.9 Statistical Methods

Descriptive statistics will be used for reporting available study results. Baseline and demographic characteristics will be presented. Continuous variables will be summarized by descriptive statistics such as mean, standard deviation, median, minimum, and maximum. Discrete variables will be summarized by frequency tables and percentages.

Adverse events will be summarized by presenting the number and percentage of patients experiencing any adverse event. Any other information collected such as seriousness, severity, and relationship to study device and procedure will be listed as appropriate.

IOP change from baseline will be summarized at each evaluation by mean, standard deviation, and range. Changes in IOP from baseline (Day 0 prior to assigned treatment) will be summarized at each visit. The proportion of subjects with an IOP reduction of 20% or more from baseline will be tallied at each post-operative visit. The number and frequency of medications will be tallied at each visit.

Slit lamp exam and fundus exam findings will be summarized at each visit using frequency and percentage.

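### The Section 3.9 responder tally also credits eyes that reach a 20% IOP reduction only after further surgery or added medication, and the second Section 1.6 endpoint, which Section 3.9 does not name, removes only the medication part

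*Combined protocol and SAP*

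**What the plan says.** Section 1.6 (headed Study Population, although it lists effectiveness endpoints) defines two responder endpoints. The first is "The proportion of subjects with an IOP reduction of 20% or more from baseline at each postoperative visit". The second is "The proportion of subjects with an IOP reduction of 20% or more from baseline after 6 months while using the same number or fewer medications". Neither mentions surgery after the laser procedure.

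Section 3.9 carries the first endpoint forward: "The proportion of subjects with an IOP reduction of 20% or more from baseline will be tallied at each post-operative visit". It treats medication separately: "The number and frequency of medications will be tallied at each visit". It does not name the second endpoint, although a general line could cover it: "Discrete variables will be summarized by frequency tables and percentages". For the baseline it says: "Changes in IOP from baseline (Day 0 prior to assigned treatment) will be summarized at each visit".

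Section 3.7.5 foresees further surgery: "If a subject requires additional glaucoma surgery, the subject will continue to be seen for the duration of the study at required follow-up visits", and gives the reason, "so that safety and effectiveness can continue to be monitored". It does not say how the IOP of such an eye enters the responder counts. Section 3.7.2 lists secondary surgical intervention among the possible postoperative adverse events. Sections 1.1.2 and 1.4 leave it to the investigator to add medication after the first month, and Appendix B.5 has IOP measured with the subject's usual medication taken.

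**The concern.** In a single-arm study the responder proportion will be read as what the laser achieved. If an eye reaches a 20% reduction only because of a second operation or an extra drug, the Section 3.9 tally still counts it as a responder. The second endpoint deals with the extra drug. It does not deal with the operation, because surgery can lower IOP without raising the medication count.

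The restricted rate can be derived later from subject-level data. The rule for re-operated eyes would then be chosen by people who have already seen which eyes it affects. With so few eyes, that choice can move the proportion visibly.

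**Working it through.** The protocol gives no sample-size derivation, target response rate or expected number of re-operations, so there is no stated figure to reproduce. The check is a classification of eyes followed by simple arithmetic.

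**Inputs.** At most 20 subjects are consented and one eye each is treated (Section 1.4). The endpoint definitions are in Section 1.6, the tally in Section 3.9 and follow-up after surgery in Section 3.7.5. I read the medication limit in the second endpoint as a comparison with the count at baseline.

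**Step 1: how each kind of eye counts if it shows a 20% reduction at the visit.**

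| Eye | Section 3.9 tally | Second endpoint as written | Second endpoint with a surgery rule |
|---|---|---|---|
| No secondary surgery, medication count not raised | responder | responder | responder |
| No secondary surgery, medication count raised | responder | non-responder | non-responder |
| Secondary surgery, medication count not raised | responder | responder | non-responder |
| Secondary surgery, medication count raised | responder | non-responder | non-responder |

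The third row is the gap that neither endpoint closes. The second row is closed by the second endpoint, provided it is reported.

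**Step 2: size.** Let *N* be the eyes treated, *b* the eyes in row 1, *s* the eyes in row 3 and *m* the eyes in rows 2 and 4.

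- Section 3.9 tally = (*b* + *s* + *m*)/*N*
- Second endpoint as written = (*b* + *s*)/*N*
- Second endpoint with a surgery rule = *b*/*N*

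The tally exceeds the last rate by (*s* + *m*)/*N*, and the second endpoint as written exceeds it by *s*/*N*. Each affected eye is worth 100/*N* points. At *N* = 20 this is 100/20 = 5.0 points. With fewer eyes it is more: if 15 were treated (an assumption), 100/15 = 6.7 points. If *s* = *m* = 0, all three rates are equal.

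**Step 3: the baseline.** Section 3.9 places the IOP baseline on Day 0 before treatment. In Appendix A, Table B, footnote 4 has the Day 0 IOP taken after surgery. The pre-treatment measurement that Table B does schedule is the diurnal IOP at the Baseline visit. The choice can decide a responder's status. With assumed values, a follow-up IOP of 19 mmHg is a reduction of (24 − 19)/24 = 20.8% from a baseline of 24, but (23 − 19)/23 = 17.4% from a baseline of 23.

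**Step 4: the follow-up value.** Section 1.1.2 lists diurnal IOP among the baseline and postoperative measurements without naming visits. Section 1.4 requires IOP at baseline, 6 and 12 months without calling it diurnal. Table B marks diurnal IOP at Baseline, Month 3 and Month 12, and a single-timepoint IOP at Month 6. Under Appendix B.5 each timepoint is a mean of two measurements, with a third if the two differ by more than 2 mmHg. The protocol does not say which value feeds the responder calculation at visits that have one kind, the other or both.

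**The case against.** The strongest reply is that the text already gives an answer: count the IOP observed at each visit, whatever else was done. Section 3.7.5 fits that reading, since it keeps re-operated subjects in view for effectiveness. An as-observed tally is a legitimate descriptive choice, and that part stands, which is why the raw tally should be kept. But the protocol does not state it as a choice, and with no comparator it attributes the effect of a second operation to the laser.

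Several stronger readings are tempting and should be resisted.

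- A reader might infer that the second endpoint has been dropped from the analysis. The documents do not support that: Section 1.6 prespecifies it, the line on discrete variables in Section 3.9 could cover it, and the medication data are collected.
- A reader might infer that the reported rate will be materially inflated. Nothing in the documents says how many eyes will be affected. An eye that misses 20% because its drops were reduced or stopped would pull the rate the other way.
- A reader might infer that the Day 0 baseline is an outright error. Text around Section 3.4 (Preoperative Care) is redacted and may provide for a pre-treatment reading, so the fair request is to reconcile the two places.
- A reader might infer that surgery late in the study would go unrecorded, because Table B marks no adverse event assessment at Month 12. Section 3.7.1 requires adverse events throughout the trial to be documented, so that does not follow.

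**Conclusion.** The point holds as a modest one. Sections 1.6, 3.7.5 and 3.9 show no redaction, and none of them says how an eye with secondary surgery counts. As written, the Section 3.9 tally credits any eye with a 20% reduction, however it was reached. The second endpoint removes eyes with added medication but not re-operated eyes whose medication count has not risen.

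Each affected eye adds at least 5 percentage points, on the basis that no more than 20 eyes are treated. The number affected is unknown and may be zero, in which case nothing changes. The objective is safety and the statistics are descriptive, so no error rate, threshold or safety conclusion is touched.

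The corrected rate should not be read as an isolated laser effect. Eyes enter on a screening IOP of 21 to 35 mmHg and there is no control arm, so regression to the mean remains under any counting rule.

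**What to change.** Amend Section 3.9 as follows.

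1. Name the second endpoint as Section 1.6 defines it and report it at Month 6 and Month 12. Count an eye as a non-responder from the date of any secondary IOP-lowering surgery in the study eye. Keep the raw tally beside it. Give per-visit counts of eyes with added medication and of eyes with secondary surgery. List paracentesis (allowed under Postoperative Instructions) and cataract surgery separately, so that their handling is not decided afterwards.
2. Reconcile the Section 3.9 baseline with Table B footnote 4. If no pre-treatment Day 0 IOP exists, use the Baseline-visit diurnal mean for the analysis.
3. Reconcile Table B with Sections 1.1.2 and 1.4 on which visits have diurnal IOP, then name the follow-up IOP used at each visit.

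These are counting and definition rules, and patient care does not change. No new data are expected. Table B records medications at Baseline and every postoperative visit, and Section 3.7.1 sends surgical treatment of ophthalmic adverse events to the Ocular Procedure Log.

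The cost is a minor protocol amendment, which needs ethics committee approval (Appendix F.6), and a possibly less favourable rate. Two limits remain. A medication count does not detect a switch to a stronger drug, and an eye that misses 20% after its drops are removed gets no credit.

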1.4 Study Design

This is a prospective, single-center, and single arm clinical trial of ViaLase Laser for the treatment of open angle glaucoma. Subjects will be screened for qualification as per the inclusion/exclusion criteria and must meet the inclusion/exclusion criteria in at least one eye to be enrolled. Up to 20 subjects will be consented as per the informed consent process. Subjects will be treated with the ViaLase Laser in one eye and followed for 12 months.

Eligible subjects will be examined preoperatively to obtain ocular and medical history and to establish a baseline ocular condition. Baseline and postoperative measurements will include distance visual acuity (best corrected), manifest refraction, intraocular pressure (IOP at baseline, 6 months and 12 months required), slit-lamp examination, gonioscopy, visual field, dilated fundus examination, specular microscopy (at baseline, 6 months and 12 months), and pachymetry.

Subjects who are on IOP lowering medications will be allowed to continue prior to laser treatment and up to one-month post-treatment. It is the investigator's discretion whether to add, continue or stop the medications after one month.

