1.5.1 Immediate Safety Outcomes

Immediate safety outcomes will be assessed during the Operative day (day-0), 1-day and 1-week visits:

- Percentage patients with elevated IOP equal or greater than 6 mmHg at 1-hour post-treatment
- Percentage of patients with iritis, anterior chamber flare and cells
- Percentage of patients with hyphema
- Percentage of patients with corneal haze

Percentage of patients with hypotony

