1.7 Study Population

1.7.1 Inclusion Criteria

The study eye must meet all the criteria below:

- Diagnosis of primary open-angle glaucoma (including pigmentary and pseudoexfoliative glaucoma).
- 2. Glaucomatous visual field defects consistent with optic nerve defects and defined as one or more of the following:
 - A cluster of 3 or more points in an expected location of the visual field depressed below the 5% level, at least 1 of which is depressed below the 1% level on the pattern deviation (PD) plot; or
 - b. Glaucoma hemi-field test "outside normal limits"

Note: Visual field reliability indices (i.e., fixation losses, false positives, and false negatives) should all be less than 33%. For subjects with a screening visual acuity of 20/100 or worse, a visual field is not required, and the above criteria do not need to be met.

- 3. Nerve abnormality characteristic of glaucoma as evaluated by clinical ophthalmoscopy defined as one or more of the following:
 - a. Diffuse thinning, focal narrowing or notching of the optic disc rim especially at inferior or superior poles.
 - b. Localized abnormalities of the peripapillary retinal nerve fiber layer, especially at inferior or superior poles.
 - c. Optic disc neural rim asymmetry of the two eyes consistent with loss of neural tissue.
- 4. Subject eye is phakic
 - a. If **phakic**, then the crystalline lens will not have visually significant cataract that is expected to require cataract surgery within next one year. Cataract will be evaluated by using the AREDS clinical lens grading system (ARLNS). Specifically, crystalline lens must have ARLNS grade of ≤ 1.5 for signs of nuclear opalescence, cortical or posterior subcapsular opacities. Lenticular opacities not characterized by the ARLNS grading system shall also be evaluated (e.g. anterior subcapsular cataracts).
- 5. Mean IOP with medication at screening between 21 mmHg and 35 mmHg, inclusive.
- 6. Iridocorneal angle anatomy defined as follows:
 - a. Trabecular meshwork visible on gonioscopy defined by Shaffer grade \geq 3.
 - b. Normal anatomy as determined by gonioscopy.
- 7. Light perception or better in the study eye at screening.

Note: The non-study eye must not have a Snellen corrected visual acuity (CVA) of worse than 20/200 at screening.

8. Age 45 years or older

- 9. Available, willing, with sufficient cognitive awareness to comply with examination procedures and schedules.
- 10. Signed written informed consent.

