3.5 Schedule of Visits and Clinical Assessments

All required clinical assessments should be performed at each scheduled visit as specified in Appendix A. Methods for performing assessments are described in Appendix B.

For interim visits, clinical assessments that are required by the protocol or as deemed necessary by the Investigator will be conducted. Assessments will be performed according to methods described in Appendix B and recorded on an interim visit CRF. Unscheduled visit clinical assessments will be conducted according to standard of care and documented on an unscheduled visit CRF.

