The subject should attempt to read each letter, line by line, left to right, beginning with line 1 at the top of the chart (20/200 line) or a line in which they can comfortably read all the letters. The subjects should be told that the chart has letters only, no numbers. If the subject reads a number, he or she should be reminded that the chart contains no numbers, and the examiner should then request a letter in lieu of the number. The subjects should be asked to read slowly, about one letter per second, to achieve the best identification of each letter. He/she is not to proceed to the next letter until he/she has given a definite response. To provide standardized and well-controlled assessment of visual acuity during the study, all visual acuity assessments for a subject must be performed consistently (e.g., the same lighting conditions, viewing distance, etc.) during the entire study. Refer to the study manual for further instruction on assessing ETDRS visual acuity.

NOTE: The study coordinator or technician can perform refractions and ETDRS visual acuity assessments if they are delegated to perform these tasks on the delegation of authority log.

B.3 Pinhole Visual Acuity (Snellen)

Pinhole visual acuity testing will be performed using an uncorrected pinhole technique using a Snellen chart at specified visits according to **Appendix A.**

B.4 Slit Lamp Exam

The slit lamp exam will be performed at the screening visit and at all postoperative visits starting with the Day 1 exam. The slit lamp exam will include the measurement of aqueous cell and flare by a standard grading system and an evaluation for the presence of corneal abnormalities, pupillary irregularities, iris atrophy and pigment dispersion.

For the evaluation of aqueous cells and flare, use the following SUN grading schemes (22):

B.4.1 Grading Scheme for Anterior Chamber Cells

Table C – Anterior Chamber Cell Grade Scheme

Grade	Cells in Field*
0	<1
0.5+	1-5
1+	6-15
2+	16-25
3+	26-50
4+	>50

^{*}Field size is a 1mm by 1mm slit beam

B.4.2 Grading Scheme for Anterior Chamber Flare

Table D – Anterior Chamber Flare Grade Scheme

Grade	Description			
0	None			
1+	Faint			
2+	Moderate (iris and lens detail clear)			
3+	Marked (iris and lens details hazy)			
4+	Intense (fibrin or plastic aqueous)			

B.4.3 Grading Scheme for AREDs 2008 Clinical Lens Opacity

- 1. Dilate pupils to at least 5 mm diameter.
- 2. Use slit lamp with approximately 10X magnification.
- 3. Use brightest beam intensity.

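### Slit-lamp and fundus findings are planned only as per-visit frequencies, so the percentage of patients ever affected and the split between new and pre-existing findings go unreported

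*Combined protocol and SAP*

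**What the plan says.** Safety is the study's stated objective (section 1.3), and the analysis is descriptive: "Descriptive statistics will be used for reporting available study results". For the two examinations at issue, section 3.9 gives one specific rule: "Slit lamp exam and fundus exam findings will be summarized at each visit using frequency and percentage". The same section summarises IOP as change from baseline, and adverse events by the number and percentage of patients with any event.

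Section 1.5.1 defines the immediate outcomes per patient, for example "Percentage of patients with hyphema", assessed on the operative day, Day 1 and Week 1. Iritis with flare and cells, and corneal haze, have the same form. Section 1.5.2 lists slit-lamp and fundus findings among the long-term safety outcomes.

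On timing, Appendix A and B.4 schedule the slit-lamp exam at Screening and at six post-operative visits: Day 1, Week 1 and Months 1, 3, 6 and 12. None is scheduled on Day 0. The dilated fundus exam is scheduled at Screening and Months 1, 3, 6 and 12. For visits outside the schedule, section 3.5 says: "Unscheduled visit clinical assessments will be conducted according to standard of care and documented on an unscheduled visit CRF".

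On size, "Up to 20 subjects will be consented as per the informed consent process", and "Subjects will be treated with the ViaLase Laser in one eye and followed for 12 months", so a percentage of treated eyes is also a percentage of patients.

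**The concern.** Two pieces of information are lost.

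The first is how many patients were ever affected. A transient effect of the laser can appear in one eye on Day 1 and in another at Week 1. Per-visit percentages do not show whether these are the same eyes. Section 3.9 also does not say whether findings from interim or unscheduled visits enter any table.

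The second is which findings are new. Entry criteria require or allow findings before treatment. Inclusion criterion 3 requires a glaucomatous nerve abnormality in every study eye, criterion 4 accepts lens opacity up to grade 1.5, and exclusion criterion 6 permits minor diabetic or hypertensive retinopathy. A post-operative prevalence mixes these with anything that arose or worsened after the laser.

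In a study of up to 20 eyes meant to give initial safety evidence, these counts are a main output.

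**Working it through.** The documents state no expected rate, precision or cumulative incidence, so there is no figure to reproduce. The rates below are assumptions, with 20 treated eyes and complete follow-up.

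**1. Eyes ever affected.** If x of N eyes show a finding at each of k exams, the number ever affected lies between x (the same eyes each time) and the smaller of N and k·x (different eyes each time). If visits were independent, the expected proportion would be 1 − (1 − x/N)^k. With N = 20 and x = 2, every per-visit table reads 2/20 = 10% (exact 95% CI 1.2% to 31.7%).

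| Exams counted | k | Lowest | Independent visits | Highest |
|---|---|---|---|---|
| Slit lamp, Day 1 and Week 1 | 2 | 2/20 = 10% | 1 − 0.9² = 19.0% | 4/20 = 20% |
| Slit lamp, all post-operative | 6 | 10% | 1 − 0.9⁶ = 46.9% | 12/20 = 60% |
| Fundus, all post-operative | 4 | 10% | 1 − 0.9⁴ = 34.4% | 8/20 = 40% |

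The exact 95% CI for 4/20 is 5.7% to 43.7%. With x = 1, six slit-lamp exams reading 5% each fit 5% to 30% ever affected.

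**2. New versus pre-existing.** If b eyes have a persistent finding at Screening and one further eye develops it, a post-operative table reads (b + 1)/20.

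- b = 2: 3/20 = 15%, against new findings of 1/20 = 5% (1/18 = 5.6% of eyes free of it at Screening).
- b = 6: 7/20 = 35%, against 5% (1/14 = 7.1%).
- Optic nerve abnormality, b = 20 by criterion 3: a present/absent count starts at 20/20 = 100% and cannot show worsening.

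**3. Does a Screening column solve it?** With a eyes positive at Screening and c at a later visit, the number newly positive lies between max(0, c − a) and min(c, 20 − a). For a = c = 4 that is 0 to 4 eyes, or 0% to 20%, although both columns read 20%. A column shows net change only.

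**4. Does the adverse event summary solve it?**

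| Finding | Adverse event rule | Left without a stated per-patient summary |
|---|---|---|
| Cells, flare, to 30 days | 3+ or 4+ (3.7.1) | 1+ or 2+ |
| Hyphema | at least 10% of the chamber (listed in 3.7.2) | under 10%, unless otherwise judged an event |
| Graded findings after 30 days | 2-grade worsening (3.7.1) | 1-grade worsening |

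Section 3.9 also states the event percentage for any event, not for each finding.

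**The case against.** The strongest reply is that the plan already has a new-or-changed, per-patient route. An adverse event is a clinically significant new or changed condition, and events are counted by patient. That stands for significant findings. It does not reach those in the last column of step 4, which include early effects that section 1.5.1 sets out to count without a severity threshold.

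It can also be said that section 1.5.1 does not spell out pooling across visits, so one percentage per visit might satisfy it. That reading is possible, but the plan would then have no figure for patients ever affected, and it should say so.

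Several stronger readings are tempting and not supported:

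- *That cumulative incidence is understated.* The tables are never presented as cumulative, and the gap is nil if the same eyes are affected throughout.
- *That pre-existing findings are counted as laser effects.* Section 3.9 refers to each visit, which plausibly includes Screening, and it specifies post-operative visits where it means only those (the IOP proportion). The Screening percentage would probably stand beside the later ones.
- *That three early exams allow up to 30%.* Section 1.5.1 names three occasions, but no Day 0 slit-lamp exam is scheduled. Parts of the operative text are redacted, so some Day 0 recording cannot be excluded or assumed.
- *That unscheduled findings are left out.* Section 3.4 requires a CRF for every exam; section 3.9 is merely silent on where they are tabulated.
- *That early inflammation is contaminated by pre-existing disease.* Active ocular inflammation is excluded at entry (section 1.7.2).
- *That pigment findings must pre-date the laser in some eyes.* B.4 looks for "pupillary irregularities, iris atrophy and pigment dispersion", and criterion 1 admits open-angle glaucoma "including pigmentary and pseudoexfoliative glaucoma". Pre-existing findings are possible, but the documents give no frequency.

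**Conclusion.** The point holds as a reporting gap. The specified tables cannot yield the percentage of patients ever affected, and they do not separate new or worsened findings from those present at Screening. The adverse event summary closes only part of this.

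The size cannot be fixed in advance. The ranges in the working rest on an assumed 2/20 at each exam, 20 treated eyes and no missing visits; observed rates will differ. Unreported cumulative incidence can make the early effects look rarer than they were, while persistent findings can make them look commoner, so there is no net direction to correct for. No hypothesis test or sample size is affected. The change should be made because safety is the study's objective and the data are already collected.

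**What to change.** In section 3.9:

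1. Name Screening as the reference for both examinations. It is the only scheduled pre-operative exam of either kind, 4 to 90 days before surgery (1 + 3 to 30 + 60 days).
2. For each slit-lamp outcome in section 1.5.1, report the number and percentage of treated eyes with a new or worsened finding at any visit through Week 1. Use Day 0 findings only where recorded.
3. For the slit-lamp and fundus outcomes in section 1.5.2, report the same at any visit to Month 12.
4. Include interim and unscheduled visits, and state the denominator.
5. Add a shift table from Screening to the worst post-laser grade for cells, flare and lens opacity, which have scales in B.4. For findings with no grading scale, classify as new or present at Screening.
6. Keep the per-visit tables as supportive.

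The cost is SAP wording and a little more programming, with no added exams or subjects. The cumulative percentages will look less favourable than the per-visit ones.
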